2.8.1.3 Acceptability analysis

Our approach to the qualitative data will involve thematic analysis and employ both inductive and deductive coding techniques.^{42,43} We will first develop an *a priori* code book that reflects key analytic concepts of *predisposing*, *enabling*, and *need* characteristics from the Andersen Behavioral Model. During the process of reading and coding of transcripts using this initial coding scheme, additional codes may be added to document emerging themes of interest.

Analysis will be led by co-I [name] and will be assisted by the experienced qualitative PHRU team. Qualitative analysis will proceed by first exploring broad patterns and experiences of study participants, and then assessing possible similarities and differences in experiences between different types of patients (including different ages, gender, level and type of care engagement, etc.) and providers (different types). Given strong gender roles in South Africa, we will specifically explore potential differences in perceptions of and experiences with intervention services among patients based on gender of the participant.

2.8.1.4 Social and medical needs analysis

We will use descriptive analysis to describe the proportion of participants with specific findings (clinical or psychosocial) or triage decisions and outcomes following that decision path. Logistic regression will be used to assess for associations between post-hospital outcomes and in-hospital medical and psychosocial measures. A multivariable model will assess for specific associations and interactions between significant factors. Sex, age, and trial arm will be included, *a priori*, in logistic regression modeling. These findings will be used to refine the list of fields on the Home Link clinical instrument and clinical algorithm.

All post-hospital assessments (Home Link visit clinical instrument (Appendix)), participant challenges identified during patient-centered counseling sessions (from structured counselor notes), triage decisions from the discharge officer, findings on laboratory testing, and clinical evaluation during inpatient or ambulatory care that Home Link arm participants receive will be abstracted from hospital or clinic paper or electronic records and the electronic National Health Laboratory Service records. These data will be organized to describe the intensity of care, psychosocial needs, clinical decision making, and most common clinical scenarios.

3 Data Management

Data will be collected to review study associated outcomes in order to evaluate the extent to which the case management goals and objectives are being met. To achieve this, data will be collected in the Home Link and Care as Usual arms. In addition to this, data will also be collected to assess actual programme performance against planned activities.

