2.4.2 Randomization

The total sample size is 180 HIV-positive and 60 HIV-uninfected adults. There will be a total of four study arms comprising of two arms for HIV uninfected and two arms for PWH. We will

perform individual randomization blocked by HIV-status to enroll 30 HIV-uninfected adults per arm and 90 PWH per arm (Figure 2).

[figure not shown]

Figure 2: Randomization Study Arms for Home Link Intervention

1. Randomization of hospital patients for recruitment: On each participant recruiting day, a list of all medical ward patients will be generated, and each patient will then be randomly listed in order of planned recruitment. Patients will be approached at any time after admission if they are next on the list for recruitment until the enrolment target is reached for that day. A new list will be generated each day including only those patients admitted 2 days prior (or on Thursday, Friday and Saturday on Mondays).
2. Randomization to study arm: After informed consent and completion of baseline CRFs the participant will be randomized to care as usual or Home Link arm.

Randomization will be conducted immediately after eligibility criteria for the participant has been documented and informed consent has been signed. Participants will be randomized 1:1 to either the care as usual or the Home Link intervention arms using computer-generated random numbers, stratified by HIV-status.

A study staff member will SMS a dedicated study telephone number – staffed by someone not linked to any other aspect of the conduct of the study. Details of the eligible participant, including randomization group (1=living with HIV; 2=living without HIV), initials (first two letters of the first name and first two letters of the surname), age, and sex, will be sent via SMS to the randomizing team. A member of the randomizing team will then relay the allocation details (within 15 minutes) to the study staff member

who requested the randomization via SMS. Proof of randomization will be sent to the study staff member who will place the proof into the participants' study file.

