Alcohol use	Alcohol use disorder identification test (AUDIT), shortened version	Baseline, 6 months	Proportion

Medical conditions and psychosocial needs will be assessed prior to hospital discharge and post-hospital by using Home Link visit and other care contact records.

a. Medical assessment prior to hospital discharge: Clinical data will be abstracted or specifically obtained for the study, if not in the clinical record: HIV viral load, CD4 count, HIV drug resistance testing, Xpert Ultra for rapid TB diagnosis, discharge diagnoses, and discharge medications.

Blood will be drawn from all participants living with HIV for drug resistance testing; however, we will only conduct the drug resistance test if the viral load result is >1000 copies/mL. We may use leftover specimen from the drug resistance test to repeat the viral load and drug resistance test using a plasma separation card in collaboration with the National Institute for Communicable Diseases (NICD).

b. Psychosocial assessment prior to hospital discharge: social support, depression, economic status, and HIV stigma will be measured. The 12-item HIV stigma scale⁴⁵ (including enacted, internalized, and anticipated stigma components), CES-D (short) depression scale, MOS social support instrument, food security, and AUDIT alcohol use instrument will be administered to participants prior to discharge (E002).

c. Post-hospital services delivered: All post-hospital assessments (Home Link visit clinical instrument (HL001), participant challenges identified during patient-centered counseling sessions (from structured counselor notes), triage decisions from the discharge officer, findings on laboratory testing, and clinical evaluation during inpatient or ambulatory care that Home Link arm participants receive will be abstracted from hospital or clinic paper or electronic records and

the electronic National Health Laboratory Service records. These data will be organized to describe the intensity of care, psychosocial needs, clinical decision making, and most common clinical scenarios.

Sampling: All participants will have in-hospital laboratory and psychosocial assessments. All participants in the Home Link arm will be included in the assessment of post-discharge needs and triage outcomes.

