3.2 Study sample size justification

We propose to recruit a sample of 240 participants randomized 1:1 into care as usual and Care Link arms. The participants will be blocked to include 30 HIV-uninfected adults and 90 people living with HIV per arm. The sample size has been determined to be feasible given time and budget limitations while still providing insight into the efficacy. Using the base rate of mortality from our preliminary study of 26% and an alpha of 0.05 and a sample size of 120 split 1:1 in care as usual and Home Link arms we have represented power versus intervention arm mortality, with sub-group analysis limited to PWH, in Table 11. We note that the primary goal is feasibility and acceptability. We are appropriately powered only for a substantial decrease in mortality from 26% to 10%.

Table 9. Power by varying effect size on reducing post-hospital mortality

alpha	power	N	N1	N2	delta	p1	p2
.05	.1589	180	90	90	-.06	.26	.2
.05	.2527	180	90	90	-.08	.26	.18
.05	.3764	180	90	90	-.1	.26	.16
.05	.5212	180	90	90	-.12	.26	.14
.05	.6704	180	90	90	-.14	.26	.12
.05	.803	180	90	90	-.16	.26	.1
.05	.9019	180	90	90	-.18	.26	.08

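### The needs model in Section 2.8.1.4 lets significance choose which factors reach interaction testing, which risks carrying chance findings and overstated odds ratios into the Home Link instrument

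*Combined protocol and SAP*

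**What the plan says.** Section 2.8.1.4 opens with a descriptive analysis of needs, triage decisions and what followed them. It then plans logistic regression of post-hospital outcomes, in the plural and not named, on medical and psychosocial measures taken in hospital. The next step is: "A multivariable model will assess for specific associations and interactions between significant factors". Sex, age and trial arm are forced in. The stated use is: "These findings will be used to refine the list of fields on the Home Link clinical instrument and clinical algorithm".

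The section lists no candidate factors. Section 2.7.4.3, item (a), names the medical measures: "HIV viral load, CD4 count, HIV drug resistance testing, Xpert Ultra for rapid TB diagnosis, discharge diagnoses, and discharge medications". Item (b) adds social support, depression, economic status, HIV stigma, food security and alcohol use. Drug resistance is tested only when viral load exceeds 1000 copies/mL.

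No section gives a significance threshold, a limit on terms, a multiplicity rule, shrinkage, internal validation or a sample-size basis for this model. Table 9 in Section 3.2 covers only the mortality comparison between arms in PWH.

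**The concern.** The least the text says is that a factor must be significant before its interactions are examined. It does not say whether significance is judged one factor at a time or jointly. Selection of this kind has two known effects. With a dozen candidates, some irrelevant factors pass by chance. Those real factors that pass tend to be the ones whose estimates came out too large. Few events make the second effect worse and raise the chance of missing a real factor.

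The model belongs to the needs work under primary objective 3 (Section 1.2), and its results have a stated use in design. The Study Summary says the pilot is to leave a protocol and procedural manual ready for a full trial. A noise factor that earns a place, or a real one passed over, could therefore influence the instrument used in that trial.

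**Working it through.** **1. The plan's own figure and the denominator.** Section 3.2 starts from: "Using the base rate of mortality from our preliminary study of 26% and an alpha of 0.05". Section 2.4.2 plans to "perform individual randomization blocked by HIV-status to enroll 30 HIV-uninfected adults per arm and 90 PWH per arm". For 26% against 10% with 90 per arm (two-sided, pooled variance, mean proportion 0.18):

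- z = [0.16 × √90 − 1.96 × √(2 × 0.18 × 0.82)] / √(0.26 × 0.74 + 0.10 × 0.90) = (1.518 − 1.065) / 0.531 = 0.85
- power = 0.803, as in Table 9

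The text of Section 3.2 mentions a sample of 120. With 60 per arm the power would be 0.63, so the table rests on 180 PWH, and that number is used here.

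**2. Expected events.**

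- Deaths in PWH at the powered effect: 90 × 0.26 + 90 × 0.10 = 32.4
- Deaths in PWH with no effect: 180 × 0.26 = 46.8
- Readmissions in PWH at the prior study's 54% (Study Summary): 180 × 0.54 = 97.2
- All 240 participants: mortality without HIV is not given. Assuming 5% to 26%, the 60 HIV-uninfected add 3 to 15.6 deaths, for a total of 35.4 to 62.4.

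**3. Number of candidates.** Six medical and six psychosocial measures make 12 at one term each. Diagnoses and medications have several categories, which would raise the count. Resistance is not available for every PWH, which would lower it. Three forced terms make 15. Twelve candidates allow 12 × 11 / 2 = 66 pairwise interactions.

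**4. Chance flags.** For independent tests at 0.05:

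- 12 null factors: 1 − 0.95^12 = 46%
- one real and 11 null factors: 1 − 0.95^11 = 43%

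The event count does not enter these formulas. Simulations agree: 40% to 47% across 32, 47 and 97 events, and 44% with 1,800 participants. Interaction tests would come on top.

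**5. Power and inflation.** Simulation of 180 PWH with 12 independent candidates, one of them real with an odds ratio of 1.5 per SD, each screened at 0.05 with sex, age and arm:

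| Events | Real factor found | Mean odds ratio when found |
|---|---|---|
| 32 | 52–53% | 1.8 |
| 47 | 64–65% | 1.7 |
| 97 | – | about 1.65 |

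Coding matters. With binary factors at 40% prevalence, a true odds ratio of 1.5 is found 18%, 21% and 25% of the time at 32, 47 and 97 events, and then averages 2.8, 2.4 and 2.3. That is a weaker effect per SD, exp(0.405 × √(0.4 × 0.6)) = 1.22, so only exaggerated estimates pass. A binary odds ratio of 2.0 is found 39%, 49% and 65% of the time and averages 3.0, 2.7 and 2.6.

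**6. Selection or sparsity?** The full 15-term model has 32.4 / 15 = 2.2 to 46.8 / 15 = 3.1 deaths per term. Fitted without selection or penalty, it gives a mean odds ratio of about 1.56 for a true 1.5 per SD. For a binary 2.0 it gives 2.1 to 2.2. Average bias is small, so the inflation in step 5 comes from selection.

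**7. Does the alternative do better?** With several real factors, ridge gave a squared error of 0.33 against 0.59 for select-then-fit at 32 deaths, and 0.27 against 0.47 at 47. With only one real factor it was slightly worse.

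**The case against.** The strongest reply is that much of this rests on choices the plan does not make. Section 2.8.1.4 does not say that the outcome is death or that the model is limited to PWH. Section 2.7.4.3 gives in-hospital assessments to all participants. The 12 candidates are inferred from that section, and 0.05 is assumed. These points stand, and the event counts are conditional on them. But viral load, CD4 count, resistance and HIV stigma apply only to PWH, so a model using them is in practice restricted to PWH. The missing outcome and population are also part of what needs fixing.

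A second reply is that objective 3 is mainly descriptive, that Section 3.2 puts feasibility and acceptability first, and that this is a pilot. That limits the weight of the point, and the descriptive part of Section 2.8.1.4 is untouched. It does not dispose of it, because the regression is not labelled exploratory and its results have a stated use.

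A third reply is that the predictors are in-hospital measures while the instrument is a home-visit form, and that no rule ties a p-value to a field. This is correct. A reader might infer that false findings will be built into the instrument or that significance decides which fields stay. The documents say only that findings will help refine the list.

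**Conclusion.** The concern holds as a risk. Letting significance choose the factors for interaction testing, with no safeguard stated, gives about a 43% to 46% chance of flagging at least one irrelevant factor. Real factors that pass are overstated: a true 1.5 per SD appears as about 1.7 to 1.8 with 32 to 47 deaths, after being found only about 50% to 65% of the time, and as about 1.65 with 97 events.

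These sizes assume 12 independent candidates with one term each, a 0.05 threshold, full outcome data and the stated effect sizes. At 90% ascertainment of vital status the deaths fall to about 29 to 42.

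Two stronger readings should be resisted. One is that the small number of deaths causes the false flags. It does not: the rate follows from the number of tests, and few deaths add low power and more inflation. The other is that 2 to 3 deaths per term makes the unpenalised model badly biased. Step 6 shows little average bias without selection. The between-arm mortality comparison is not affected. The change is worth making because it costs almost nothing.

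**What to change.** In Section 2.8.1.4, replace the sentence on the multivariable model with:

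> For each named outcome (six-month death; readmission), a list of factors fixed on clinical grounds before outcome data are analysed will enter one penalised (e.g. ridge) logistic model with sex, age and arm. HIV-specific measures will be modelled in PWH only; HIV status will be added when all participants are modelled. Neither factors nor interactions will be selected by p-value; any interaction examined will be pre-listed. Estimates will be shown with 95% intervals and labelled exploratory.

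Then add:

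> No instrument field will be added or dropped on statistical significance alone.

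The list should say how multi-category measures are coded and how resistance, missing by design at low viral load, is handled. The method for the intervals should be named, since those around shrunken estimates are approximate. Measures left off the list can still be described without testing.

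The cost is a little more programming, fewer factors given a formal test, and slightly worse estimates than selection if only one factor truly matters. No new data or participants are needed.

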2.3 Study Population

The population is comprised of adults (≥ 18 years old), either male or female, spending at least two nights in a medical ward of Tshepong Hospital. We will only include individuals with known HIV status, either HIV-positive or HIV-negative. We propose to recruit up to 180 HIV-positive and 60 HIV-uninfected participants.

Randomization to the intervention vs control arms will be stratified by HIV status.

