2.3.1 Inclusion criteria

- Tested for HIV (can be living with HIV or HIV-uninfected) – HIV negative participants should have a documented test from within the previous 3 months
- Residing within Matlosana sub-district
- Agree to post-discharge follow-up including home visit
- Able to provide informed consent or, if lacking capacity at the time of recruitment (if unable to answer basic orientation questions including name, month/year, and residence location), as determined by the study team, having a next of kin able to provide informed consent

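### The needs regression should force in HIV status, and should fit the HIV-only measures in a separate model of people with HIV

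*Combined protocol and SAP*

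**What the plan says.** Section 2.8.1.4 describes two steps. First: "Logistic regression will be used to assess for associations between post-hospital outcomes and in-hospital medical and psychosocial measures". Then: "A multivariable model will assess for specific associations and interactions between significant factors". The adjustment set is fixed in advance: "Sex, age, and trial arm will be included". The section gives no list of candidate measures, no analysis population by HIV status, no rule for missing values and no code for a measure that does not apply to a participant.

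The measures are listed in section 2.7.4.3. Item (a) covers CD4 count, viral load, drug resistance, Xpert Ultra, and the diagnoses and medications at discharge. Blood for resistance testing is taken from PWH only, and "we will only conduct the drug resistance test if the viral load result is >1000 copies/mL". Item (b) covers the psychosocial scales. The sampling paragraph adds: "All participants will have in-hospital laboratory and psychosocial assessments".

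On the design, section 2.3 says: "Randomization to the intervention vs control arms will be stratified by HIV status". Section 2.4.2 sets 90 PWH and 30 HIV-uninfected participants per arm, which makes 180 and 60.

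**The concern.** Two gaps arise from the same paragraph.

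- **Confounding by HIV status.** The one factor that the design treats as important enough to stratify on is missing from the forced set. Xpert result, discharge diagnoses and discharge medications can all be expected to differ between PWH and others; antiretroviral drugs on the medication list are a direct marker of HIV. In a pooled model without HIV status, such a measure can appear to predict outcome only because it identifies who has HIV.
- **Measures that exist in a subset.** Viral load has no value in an HIV-uninfected participant. Resistance has no value there, nor in PWH at or below 1000 copies/mL. Most regression software deletes a record with a blank predictor unless told otherwise, so adding one of these measures can change the population being analysed without anyone having decided to change it.

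Characterizing needs is primary objective 3 (section 1.2). Section 2.8.1.4 says that the findings will be used to revise the home-visit instrument and its algorithm, and the Study Summary presents the pilot as preparation for a full trial. A confounded or unintentionally restricted association would be carried into that work.

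**Working it through.** **1. The plan's own figure.** The plan gives no sample size, event count or power for this model. The nearest figure is in section 3.2, Table 9: power 0.803 for mortality of 26% versus 10% with 90 PWH per arm. With pooled variance under the null and two-sided alpha 0.05:

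z = [0.16 × √90 − 1.96 × √(2 × 0.18 × 0.82)] / √(0.26 × 0.74 + 0.10 × 0.90) = (1.518 − 1.065) / 0.531 = 0.852, so power is 0.803.

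It reproduces. Below, 26% and the two-arm mean (26% + 10%) / 2 = 18% serve as two mortality scenarios.

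**2. Records kept under default deletion.** The documents do not give the share of PWH above 1000 copies/mL. I assume 30%, 50% and 70%.

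| Model contains | Records kept | Share of 240 | Deaths at 26% | Deaths at 18% |
|---|---|---|---|---|
| Viral load | 240 − 60 = 180 | 75% | 46.8 | 32.4 |
| Resistance, 30% above 1000 | 180 × 0.30 = 54 | 22.5% | 14.0 | 9.7 |
| Resistance, 50% above 1000 | 180 × 0.50 = 90 | 37.5% | 23.4 | 16.2 |
| Resistance, 70% above 1000 | 180 × 0.70 = 126 | 52.5% | 32.8 | 22.7 |

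Deaths are records × mortality. With only five terms (sex, age, arm and two measures), the resistance rows give 14.0/5 = 2.8 to 32.8/5 = 6.6 deaths per term at 26%, and 9.7/5 = 1.9 to 22.7/5 = 4.5 at 18%.

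A model with sex, age, arm and one measure taken in everyone keeps all 240. Adding HIV status to it still keeps all 240. Fitting such models to a simulated 180 + 60 data set gave the same counts: 240 with and without HIV status, 180 with viral load, and 126 with resistance when 70% were above 1000.

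**3. How much HIV effect could be carried.** The documents give no mortality for HIV-uninfected participants, so this is an illustration. Take 26% in PWH and assume 10% to 26% in the others. The odds ratio for HIV is (0.26/0.74) divided by the odds in the others:

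- 10%: 0.351 / 0.111 = 3.2
- 15%: 0.351 / 0.176 = 2.0
- 20%: 0.351 / 0.250 = 1.4
- 26%: 0.351 / 0.351 = 1.0

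A measure with no effect of its own that tracked HIV status perfectly would show the whole of this ratio in a pooled model without HIV status. One that tracks it partly would show part of it. If mortality does not differ by HIV status, nothing is carried.

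**The case against.** The strongest reply is that the plan has not committed itself to any of this. Section 2.8.1.4 does not require viral load, resistance or stigma in the multivariable model and does not prescribe complete-case analysis. The model is to address factors found significant, so resistance enters only if it qualifies. HIV status is known for everyone and could be a candidate factor; not being forced in is not the same as being excluded. Objective 3 is also met by the descriptive analysis in the section's first sentence. The outcomes are not only deaths: at the 54% readmission of the prior study (Study Summary), 54 to 126 records would give about 29 to 68 events.

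Most of this stands, and it rules out some stronger readings:

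- A reader might infer that the model as written drops every HIV-uninfected participant. It does not. That loss needs an HIV-only measure in a pooled model and default deletion, and several listed measures are not restricted to PWH.
- A reader might infer that CD4 count and the stigma scale exist only in PWH. The stigma scale is HIV-specific in content, but section 2.7.4.3 restricts neither to PWH.
- A reader might infer, from the inclusion of patients "if lacking capacity at the time of recruitment", that psychosocial scores will be missing in the sickest and need imputing. Section 5.2 foresees participants becoming able to consent later, the scales are given at any time before discharge, and no count is stated. Imputing scores for people who could not answer would also lean on a group with few observed values.

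What the reply does not remove is the fixed adjustment set. Having named the covariates to be kept regardless of the data, the plan leaves out the stratification factor, and nothing in the section requires HIV status to be tried or retained.

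**Conclusion.** The point holds as an omission with a definite remedy, not as an error that must occur. The missing HIV status in the forced set is a matter of record. The bias that it could cause depends on two things the documents do not give: how far outcomes differ by HIV status, and how closely a measure tracks it. The loss of records is conditional on an HIV-only measure entering a pooled model under default deletion: 25% of the sample with viral load, and 47.5% to 77.5% with resistance (100% minus the 52.5% and 22.5% above), on the assumed 30% to 70%. All counts assume full enrolment and no other missing data.

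This is an improvement to an exploratory analysis. The comparison of six-month mortality by arm does not use this model and is not touched.

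**What to change.** Revise section 2.8.1.4 to specify two models:

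1. **All participants.** Force in HIV status together with sex, age and arm, and admit only measures defined for everyone. This can use all 240.
2. **PWH only.** Keep sex, age and arm, and enter the HIV-specific measures here. Code resistance as one variable with three levels: viral load at or below 1000 copies/mL; above 1000 without resistance; above 1000 with resistance. Participants at or below 1000 then stay in, so the model can use up to 180 rather than 54 to 126, provided the viral load and, where required, the resistance result are available.

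List the measures that belong to each model, and report the number of records used in each.

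The cost is a few sentences and modest programming. No new data are needed: HIV status is established at screening and sent with each randomization request (section 2.4.2), and viral load and resistance are already to be obtained under section 2.7.4.3.
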